9.3.1.4 Causality Assessment

Causality assessment, the methodology used to estimate the probability of attributing an adverse reaction, a suspected adverse reaction, or an observed adverse event to a drug, investigational drug, or investigational product, considers probabilistic categories based on the available evidence and the quality of the information, in accordance with national pharmacovigilance regulations. [54] As a tool to facilitate the probabilistic categorization of causality, the principal investigator may use the Karch and Lasagna algorithm , modified by Naranjo, which rates different items to assign a value to the cause-effect relationship between the administration of the drug and the adverse reaction. [57] See Table 6Karch and Lasagna algorithm modified by Naranjo

No .	Reagent	Score	
		Yea h	No
1.	There are conclusive previous reports on adverse drug reaction, adverse event or suspected adverse drug reaction	+1	0
2.	The adverse event occurred when the suspected drug was administered	+2	-1

Karch and Lasagna algorithm modified by Naranjo			Score
No .	Reagent	Yea h	No
3.	The adverse drug reaction, adverse event, or suspected adverse drug reaction improved upon discontinuation or administration of a specific antagonist	+1	0
4.	The adverse drug reaction/adverse event/suspected adverse drug reaction recurred upon administration of the investigational drug/investigational product/investigational drug	+2	-1
5.	There are alternative causes that can provoke this reaction.	-1	+2
6.	The adverse reaction/adverse event/suspected adverse drug reaction occurred after placebo administration	-1	+1
7.	The drug was determined in blood or other fluids in toxic concentrations	+1	0
8.	The intensity of the adverse reaction/adverse event/suspected adverse drug reaction was greater with higher doses or less with lower doses	+1	0
9.	The patient has had similar reactions to the investigational drug/product or investigational drug in the past	+1	0
10.	The adverse reaction/adverse event/suspected adverse drug reaction was confirmed with some objective evidence	+1	0
Total score			Addition

Probabilistic category based on the score obtained

Yo	The causal relationship is verified	$\geq, 9$
II	The ADR is likely due to the investigational drug or product	5 to 8
III	The ADR may be due to the investigational drug or product	1 to 4
IV	The causal relationship is doubtful	0

The items considered by the Karch and Lasagna algorithm , modified by Naranjo, are shown. Each item receives a defined score, and the final sum allows estimating the probabilistic category of the cause-effect relationship between the administration of the investigational drug/product/drug and the adverse reaction, adverse event, or suspected adverse reaction. Note that if the information is unavailable, a score of zero is recorded.

Table 6Karch and Lasagna algorithm modified by Naranjo

Thus, the degree of certainty for establishing the investigational product or investigational drug (as applicable) as the causal agent of the harmful event occurring to the participating patient may be indicated directly by the principal investigator based on their clinical experience or through the voluntary application of the aforementioned tool. However, it is important for the investigator to consider the following arguments in favor of a causal relationship:

- a) Strength of association that refers to the number of cases in relation to those exposed.
- b) The consistency of the data, that is, the presence of a common characteristic or pattern.

- c) The exposure-effect pattern: which determines the relationship with the site of onset, time, dose and reversibility after suppression.
- d) Biological plausibility: refers to the possible pharmacological or pathophysiological mechanisms involved in the development or presentation of the adverse event.
- e) Experimental findings: for example, the appearance of anomalous metabolites or high levels of drug or its biotransformation product.
- f) Analogy: experience acquired with other related drugs, adverse reactions frequently produced by the same family of pharmacological agents.
- g) Nature and characteristics of the data: objectivity, accuracy and validity of the relevant documentation. [58]

9.3.2 Sponsor Responsibilities

The sponsor will be responsible for and cover the costs arising from medical care for adverse events related to the investigational product (see section 11. Financing and insurance).

9.4 Audit

To ensure compliance with GCP and all applicable regulatory requirements, Laboratorios Sophia , SA de CV may conduct a quality assurance audit. Regulatory agencies and research and ethics committees may also conduct an inspection of this study.

9.4.1 Pre-study audit

The research centers included in the study will be subject to a pre-study visit prior to center selection, where they will be verified to meet the minimum requirements indicated by the sponsor.

9.4.2 Audit/Inspection during the conduct of the study

They may take place at any time before, during, or after the conclusion of the study. If an audit or inspection is conducted, the researcher and the institution must agree to allow the auditor/inspector direct access to all relevant documents and must allocate their own and staff time to the auditor/inspector to discuss the findings and any pertinent issues. If the audit is conducted by a regulatory agency or committee, the researcher must notify the auditor/inspector immediately.

10. Ethical considerations

10.1 Approval of committees

This study will be conducted in accordance with the standards of the “Declaration of Helsinki”, World Medical Association 2013. “Nuremberg Code”; Nuremberg Trial by the International Tribunal of Nuremberg , 1947. “Belmont Report”, National Commission for the Protection of Subjects of Biomedical and Conduct Research, 1979. It will be conducted in accordance with the scientific and technical requirements necessary for the registration of medicines for human use of the “International Conference on Harmonization” (The International Council for Harmonisation (ICH) Guideline for Good Clinical Practice. “International Ethical Guidelines for Biomedical Research Involving Human Subjects of the Council for International Organizations of Medical Sciences ” of Medical Sciences , CIOMS, 2002). “International Ethical Guidelines” for Epidemiological Studies of the Council for International Organizations of Medical Sciences of Medical Sciences , CIOMS, 2008).

The Research Ethics Committee and the Research Committee will evaluate the protocol before conducting the study and will issue their approval or any possible modifications for its

implementation. These Committees must be notified of any significant changes to the protocol. In addition to the above, the current regulations issued by the Ministry of Health must also be complied with. General Health Law, NOM 012 Mexican Official Standard NOM-012-SSA3-2012, which establishes the criteria for the execution of health research projects in human beings. The study is considered research with greater than minimum risk according to the Regulations of the General Health Law on Health Research, Title Two, Chapter I, Article 17, Category III, published in the Official Gazette on January 6, 1987.

The principal investigators, study coordinators or personnel authorized by the sponsor will submit for evaluation by the Research Ethics Committees, Research Committees, and when applicable, the Biosafety Committee, the essential documentation of the research project: research protocol, informed consent letter, researcher's manual, subject diary, as well as those requested, additionally, in accordance with the local, national or international requirements applicable by the regulatory entities.

The study will not be initiated at the research site without the confidentiality agreements and financial proposals from each of the principal investigators, duly signed, and without having previously obtained the favorable opinion and/or approval of the corresponding Research Ethics Committees, Research Committees, and, when applicable, the Biosafety Committee.

The study will not begin without meeting the relevant local, national, or international regulatory requirements and obtaining the appropriate health authorization.

10.2 Amendments to the protocol

The amendment process will be relevant when there is a need to make any changes to a document that is part of the research project or protocol, due to changes in the methodological structure, replacement of the principal investigator, or the identification of risks to the research subjects. Documents that may be amended include: the protocol, informed consent letter, researcher's manual, patient documents, measurement scales, and activity schedule.

Any amendment must be approved by the sponsor and/or the principal investigator. The amended document(s), once reviewed and approved by the Research Ethics Committee and the Research Committee or, when applicable, by the Biosafety Committee (entities that issued the initial favorable opinion for the conduct of the research), will be sent for authorization by the relevant regulatory entity.

Amendments that substantially modify the protocol or impose additional or different risks on research subjects must be approved by the aforementioned Committees. It is the investigator's responsibility to take measures in situations requiring immediate action to prevent unnecessary harm to study participants.

The principal investigator is responsible for communicating to the Research Ethics Committee any amendments to the protocol that could affect the rights, safety, or well-being of the research participants. They must also report any situation or new knowledge that indicates an increased risk to the participants, the premature termination or suspension of the study, the reasons for it, and the results obtained to that point. They must also report the conclusion of the study upon completion of the research protocol.

The list of amendments, and where necessary, the list of errata issued, will be included in the final research report.

10.3 Consent

10.3.1 Obtaining

Informed consent must be obtained before the subject undergoes any procedure indicated in the protocol.

Written consent documents will incorporate the elements of informed consent described in the Declaration of Helsinki and the ICH Guidelines for Good Clinical Practice and will be in compliance with all applicable laws and regulations.

The IP will provide the potential participant with all information regarding the characteristics of the study, its potential benefits, risks, objectives, and procedures.

This information will be provided in a language understandable to the subject. The subject will be explained that they have the right to discontinue their participation in the study at any stage, without affecting their relationship with the researcher and/or their future participation. Informed consent will be presented to the potential participant; they must have sufficient time to review each and every aspect mentioned above. Any questions they may have will be clarified by the person responsible for obtaining informed consent.

Once the participant agrees to participate in the study, he or she must sign and date the informed consent letter in the presence of two witnesses, whether or not related to the study subject. These witnesses will participate in the informed consent process and sign, confirming that the process was carried out prior to any study procedure, that the study information was clearly explained, and that any questions were clarified.

In the event that a subject is illiterate, acceptance will be with his or her fingerprint, and in the event that the subject is not capable of providing adequate written informed consent, a "legally authorized" representative of the subject may provide such consent for the subject in accordance with applicable laws and regulations.

The IP must also sign and date this consent.

Informed consent must be signed in duplicate by all parties involved, and two witnesses. One copy will be filed in the subject's file and the other will be given to the participant. The PI must document the date the informed consent was signed in the subject's medical record.

10.3.2 Special considerations

The auxiliary studies that will be performed during the study (laboratory tests) do not pose an additional risk that should be considered apart from the procedures listed in the informed consent.

10.3.3 Modification to informed consent

Changes to the "informed consent" constitute an amendment to this document and must be submitted for approval to the Research Ethics Committees and, if applicable, to the Competent Authorities.

The amendment shall include a copy of the new version in the language(s) of the country.

Such amendments may be implemented only after obtaining written approval from the Research Ethics Committee and the Regulatory Body (as applicable), except for an amendment that is required to eliminate an immediate danger to the study subjects.

Each subject affected by the amendment must complete, date, and sign two originals of the new version. The subject will be given one signed original of the amendment, and the researcher will retain the second original.

10.5 Declaration of interests

The IP agrees to declare his or her financial interests and conflicts of interest prior to the start of the study.

10.6 Access to information

The final study database will be the property of Laboratorios Sophia , SA de CV, and access to it will be restricted. The PI will not have access to it except with prior written authorization from the sponsor.

10.7 Ancillary and post-study care

Once the study is completed and adverse events are closed according to section 9.3 Adverse events, the sponsor will not extend care to the research subject.

10.8 Biosecurity aspects

NO BIOSECURITY IMPLICATIONS

The present protocol, entitled: "Phase I clinical study to evaluate the safety and tolerability of PRO-165 ophthalmic gel versus Artelac ® Nightime Gel, on the ocular surface of ophthalmologically and clinically healthy subjects", and number:SOPH165-0217/I IT HAS NO BIOSECURITY IMPLICATIONS, since no infectious-contagious biological material will be used; pathogenic strains of bacteria or parasites; viruses of any type; radioactive material of any kind; genetically modified animals and/or

cells and/or plants; toxic, hazardous, or explosive substances; or any other material that puts the health or physical integrity of the research center staff or research subjects at risk, or affects the environment. It is also declared that no cell, tissue, or organ transplant procedures, or cell therapy, will be carried out in this project, nor will laboratory, farm, or wildlife animals be used.

10.9 Final report and publication of results

10.9.1 Final report

Once the statistical analysis is completed, a final report will be written with the results obtained, by the Scientific Committee of the Clinical Operations Department of Laboratorios Sophia , SA de CV. This report will be prepared following the recommendations of the *ICH E3 Step 4 Guide*.

10.9.2 Communication of results

Regardless of the results of the study, Laboratorios Sophia , SA de CV, is committed to communicating the final report of the study to the principal investigators and the corresponding regulatory entities in the countries with participating research centers. The company maintains at all times the rights to publish and disclose the information contained therein.

10.9.3 Publication of results

Laboratorios Sophia , SA de CV, acting as the sponsor of the study, assumes full responsibility for its role and retains exclusive property rights over the study results, which it may use in any manner it deems appropriate.

The PI agrees not to publish or communicate data collected only in one center or in part of the centers before the publication of the complete results of the study, unless there is prior written agreement from Laboratorios Sophia , SA de CV.

Any draft publication and/or communication related to the study and/or the results obtained during or after the study's completion must be submitted to the participating physician researchers at least 30 days in the case of a publication and 15 days in the case of an abstract, before the scheduled date for the communication and/or presentation of a publication. The physician researchers must comment on the draft within 15 days in the case of a publication and 7 days in the case of an abstract, from the date the draft is received.

However, if the sponsor is in the process of filing a patent application for the results of the study, the sponsor may delay publication or communication of the study results until the date of registration.

11. Financing and insurance

11.1 Compensation to study participants

Subjects participating in the study will not receive financial compensation for their participation. However, subjects will receive travel expenses for each scheduled visit they attend on time. This amount, as well as the amount, will be specified in the informed consent form.

14.1 Ocular comfort index

Eye Comfort Index

Identification card	Date: / /
Study No.: SOPH172-0919-I	Subject No.: 172-_____
Subject's initials: _____	

Directions:

This questionnaire was designed to rate the comfort of your eyes.

For each question, circle your answer.

Example: In the past week, how often were your eyes red?

Never	0	1	2	3	4	5	Always	6
--------------	---	---	---	---	---	---	---------------	---

There are no right or wrong answers. Don't spend too much time on each question.

1 In the past week, how often did your eyes feel *dry* ?

Never	0	1	2	3	4	5	Always	6
--------------	---	---	---	---	---	---	---------------	---

When your eyes felt *dry*, how severe was the sensation usually?

I haven't felt it	0	1	2	3	4	5	Severe	6
--------------------------	---	---	---	---	---	---	---------------	---

2 In the past week, how often did your eyes feel *gritty* ?

Never	0	1	2	3	4	5	Always	6
--------------	---	---	---	---	---	---	---------------	---

When your eyes felt *gritty*, typically, how intense was the sensation?

I haven't felt it	0	1	2	3	4	5	Severe	6
--------------------------	---	---	---	---	---	---	---------------	---

3 In the past week, how often did your eyes feel *throbbing* ?

Never	0	1	2	3	4	5	Always	6
--------------	---	---	---	---	---	---	---------------	---

When your eyes felt like *they were stinging*, how intense was the sensation usually?

I haven't felt it	0	1	2	3	4	5	Severe	6
--------------------------	---	---	---	---	---	---	---------------	---

4 In the past week, how often did your eyes feel *tired* ?

Never	0	1	2	3	4	5	Always	6
--------------	---	---	---	---	---	---	---------------	---

When your eyes felt *tired*, how intense was the feeling usually?

I haven't felt it	0	1	2	3	4	5	Severe	6
--------------------------	---	---	---	---	---	---	---------------	---

Sheet 1 of 2

5 In the past week, how often did your eyes feel *sore* ?

Never

0 1 2 3 4 5 6 Always

When your eyes felt *sore*, how severe was the sensation usually?

I haven't felt it

0 1 2 3 4 5 6 Severe

6 In the past week, how often did your eyes feel *itchy* ?

Never

0 1 2 3 4 5 6 Always

When your eyes felt *itchy*, how intense was the sensation usually?

I haven't felt it

0 1 2 3 4 5 6 Severe

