6.3 Intervention

6.3.1 Treatments administered

6.3.1.1 Treatment under study

- **PRO-165**
 - Active ingredients (lubricant): sodium hyaluronate 0.2%
 - Pharmaceutical form: Ophthalmic gel
 - Prepared by: Laboratorios Sophia , SA de CV
 - Dosage: One drop of gel, 4 times a day during the waking period, in the fornix of the right eye.

- Formulation description: Clear gel, free of visible particles.
- Packaging description: Sterile multi-dose tube, low-density polyethylene and aluminum polylaminate with high-density polyethylene cap.

Table 4Qualitative -quantitative formulation of PRO -165

Agent type	Amount mg/ mL	Function
Sodium hyaluronate	2.0	Active ingredient
Chondroitin sulfate	Not shown	Viscosant
Polyoxylated Castor Oil 35	Not shown	Solubilizer
Polyethylene glycol 8000¹	Not shown	Cosolvent
Eddate disodium dihydrate	Not shown	Chelating agent
Cetrimide	Not shown	Conservative
Glycerin	Not shown	Osmoregulator
Sodium hydroxide	Not shown	pH adjustment
Homopolymer carbomer type B²	Not shown	Gelling agent
Polycarbophil³	Not shown	Gelling agent
Water for the preparation of injectables cbp⁴	Not shown	Vehicle

Qualitative and quantitative formulation of the investigational product PRO-165. The concentration of the active ingredient is shown, as well as the substances that act as additives. (1) Synonym of Carbowax® (2) Synonym of Carbopol® 974P NF Polymer, USP (3) Synonym of Noveon® AA-1 Polycarbofil, USP (4) as much as is sufficient for

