6.4.3.1 Visual capacity

Visual acuity (VA) is a test of visual function. Spatial visual acuity is the ability to distinguish separate elements of an object and identify them as a whole. It is quantified as the minimum angle of separation (located at the nodal point of the eye) between two objects that allows them to be perceived as separate objects.

Snellen notation is described as the distance at which the test is performed divided by the distance at which the letter is vertically equivalent to 5 minutes of arc. Thus, at 6 meters, a letter 6/6 (20/20) is equivalent to 5 minutes of arc, a letter 6/12 (20/40) is equivalent to 10 minutes, and a letter 6/60 (20/200) is equivalent to 50 minutes. The Snellen fraction can also be expressed as a decimal (i.e., 20/20 = 1 and 20/40 = 0.5). [43]

VA will be assessed at baseline, without refractive correction, using the Snellen chart. This chart will be placed in a location with adequate natural or artificial lighting and at a distance of 3 m from the subject being assessed. Visual acuity will be measured in each eye, starting with the right eye (RE),

asking the subject to keep both eyes open and using an occluder to cover the left eye (LE); the subject will read aloud the lines indicated by the evaluator. The evaluator will record the smallest line of letters visible as the RE VA in the clinical record. The LE is then assessed using the same method.

The subject's best refractive correction will then be performed, and the examination will be repeated using the obtained refraction. This result will be reported as CV, entered as a fraction in the clinical record and on the Case Report Form (CRF), and will also be entered as a decimal on the CRF. By definition, the CV cannot be less than the VA.

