6.4.3.2 Eye comfort index

This questionnaire is designed to measure ocular surface irritation using Rasch analysis to produce estimates on a linear interval scale (scores: 0–100). Similar to the index for ocular surface diseases, the Ocular Comfort Index (OCI) assesses symptoms. The OCI contains six items that focus on discomfort associated with the ocular surface. Each of these questions has two parts, which separately inquire about the frequency and severity of symptoms. [44]See Appendix 14.1 Eye comfort index

The evaluator will give the questionnaire to the subject and allow them to answer it calmly without any pressure or coercion. They will only assist them if they have difficulty understanding any of the questions.

Ocular surface stains

- *Lissamine green staining* .

A drop of topical anesthetic will be instilled into the conjunctival fornix. A second drop will then be applied to the tip of the lissamine green strip and allowed to run into the fornix. It is essential to rapidly assess the staining, sequentially, first in the OD and then the OS, so that the observed patterns are equally bright. [19]See Appendix 14.2 Oxford Scale

- *Fluorescein staining*.

A drop of topical anesthetic will be instilled in the conjunctival fornix. A second drop will then be applied to the tip of the fluorescein strip and allowed to run into the fornix. It is essential to rapidly assess the staining, sequentially, first in the OD and then the OS, so that the observed patterns are equally bright. This assessment will be performed using a cobalt blue filter. [19]See Appendix 14.2 Oxford Scale

For both stains, the value obtained according to the Oxford scale will be recorded in the CRF.

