6.6.1 Sample size calculation

There are no references on the calculation of the sample size in phase I studies, and the formulation of Humylub Ofteno® has not reported any adverse events in its periodic safety reports. Therefore, it was considered appropriate to base the calculations on previous phase I studies conducted by Laboratories . Sophia , SA de CV [45, 46, 47, 48].

The calculation was based on the adverse event presentation reported by Christ T., in a randomized, single-blind, parallel-group controlled clinical trial evaluating the efficacy and tolerability of a 5% dexamphenol ophthalmic gel versus a 5% panthenol ointment in 48 subjects with corneal erosion, UV-induced keratoconjunctivitis, or similar conditions. The intervention consisted of applying 1 cm of the gel and ointment for 4 and 3 days, respectively.[49]

The percentage of good tolerance reported with the gel was 25%, so it is expected that no more than 10% of subjects will report poor tolerance with the formulation proposed in this protocol.

The sample size was calculated using the formula for proportions

$$n = p (1 - p) \left(\frac{Z_{1-\alpha} + Z_{1-\beta}}{p - p_0 - \delta} \right)^2$$

With a statistical confidence of 95% corresponding to type I error, equal to 1.96, with a power of 90%, corresponding to type II error, equal to 0.84.

According to the previous calculation, the result is 26 subjects, which was increased by 20% to account for probable losses. The total required sample size is **32 subjects** . Therefore, each group will consist of 16 subjects, each of whom will contribute an eye to the analysis.

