For adverse event reporting, all eyes of participants randomized to an intervention group after the baseline visit will be considered. Results will be expressed as the number of cases (eyes).

The final results report will be displayed in tables or graphs, as appropriate.

The investigational drug will be considered safe and tolerable when there are no clinical or statistical differences in all primary outcome variables compared to its comparators.

Subjects with an adherence rate greater than 60% will be included in the statistical analysis to meet the study objective, based on the subject's diary. However, even if the subject's diary indicates adherence greater than 60%, if the adherence calculated by weight is less than 30%, the subject will not be included. The minimum dose necessary to obtain a pharmacological effect (lubricant/1 gel application per day) and the presence of adverse events (exposure) were considered sufficient to meet the overall design objective, in accordance with the pharmacological characteristics of the investigational product.

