9.3.1.1 Recording adverse events on the Case Report Form

The adverse event registry considers information concerning the participating patient's identification data such as code, age, sex, left eye, right eye.

Information about the type of adverse event, adverse reaction, or suspected adverse reaction to the investigational product or study drug, as applicable. The date on which the adverse event occurred is reported, as well as the date on which the Investigator became aware of it, and the date of resolution or outcome, as applicable. The clinical diagnosis is indicated. Include among concomitant medications the therapy used for the pharmacological management of the adverse

event, suspected adverse reaction, or adverse reaction. Record the outcome or resolution of the event: patient recovered without sequelae, with sequelae, or not recovered. Patient who died due to the adverse reaction/adverse event; patient who died and it is judged that the drug may have contributed; patient who died and the death was not related to the investigational product or drug; or indicate that the consequence of the event is unknown.

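### The primary tolerability score asks about both eyes although only the right eye is treated, so the untreated eye may dilute a difference between the gels

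*Protocol*

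**What the plan says.** Protocol 6.3.1.1 gives the test gel as "One drop of gel, 4 times a day during the waking period, in the fornix of the right eye"; 6.3.1.2 gives the reference gel in the same way. In 6.6.1 the subjects are described as "each of whom will contribute an eye to the analysis".

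Protocol 6.4.1.1 and the SAP list of outcome variables name the ICO as the only primary tolerability variable. SAP Table 2 tests it between groups (Mann-Whitney) and within group (Wilcoxon). On the form in Protocol 14.1, repeated in the SAP annex, all six items begin "In the past week, how often did your eyes feel", and the directions and the worked example also speak of the eyes in the plural.

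Protocol 6.4.3.2 has the subject complete the form alone; of the evaluators it says "They will only assist them if they have difficulty understanding any of the questions". The visit procedures (6.5.1.2, 6.5.1.4) only refer back to that section, and SAP Table 2 adds nothing about the eye.

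Elsewhere the protocol separates the eyes. For acuity: "Visual acuity will be measured in each eye". For both stains: "It is essential to rapidly assess the staining, sequentially, first in the OD and then the OS". The adverse-event record holds "identification data such as code, age, sex, left eye, right eye".

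Under Protocol 8.3.1 the product is "considered safe and tolerable when there are no clinical or statistical differences in all primary outcome variables". The SAP has the same rule, with *and* in place of *or*.

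**The concern.** Treatment and analysis are by eye; the primary tolerability score is by person. A subject who reads the question as covering both eyes has understood it correctly, so the evaluator has no reason to step in. The answer may then mix a treated eye with one that received nothing.

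The left eye is untreated in both arms, so whatever it contributes is unrelated to the product. It can only blur a real difference between the gels. In a trial that sets out to show a difference, that would work against the sponsor. Here the favourable conclusion follows from finding no difference, so the same blurring makes it easier to call the product tolerable.

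**Working it through.** **Is there a limiting instruction anywhere?** The places where one could stand are the form's directions and items (Protocol 14.1, SAP annex), the administration text (Protocol 6.4.3.2), the visit procedures (6.5.1.2 and 6.5.1.4) and the ICO row of SAP Table 2. None names an eye or defines an eye-specific ICO score.

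**Is there a plan figure to reproduce?** Not for the ICO. The sample size (26, then 26 × 1.2 = 31.2, rounded up to 32, or 16 per group) comes from a formula for proportions. The documents give no ICO standard deviation, expected difference or power. What follows is an illustration under stated assumptions.

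**Inputs.** From the documents: 16 per arm, alpha 0.05 (taken as two-sided), Mann-Whitney as in the SAP (with two groups the protocol's Kruskal-Wallis is equivalent). Assumed: a treated-eye difference of 1.0 SD, a left eye unaffected by arm, and a between-eye correlation rho.

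**Averaging, by formula.** If the answer is the mean of two eyes, each with SD 1, the difference halves to 0.5 and the SD becomes √((1 + rho)/2). The standardised effect is 0.5 / √((1 + rho)/2).
- rho = 0.5: 0.5 / 0.866 = 0.577
- rho = 1: 0.5 / 1 = 0.50

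Normal-approximation power is Φ(d·√(n/2) − 1.96), with √(16/2) = 2.828.
- Treated eye, d = 1: Φ(0.868) = 81%
- Average, rho = 0.5: Φ(0.577 × 2.828 − 1.96) = 37%
- Average, rho = 1: Φ(0.50 × 2.828 − 1.96) = 29%

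**Simulation with the rank test** (normal scores). A shared shift is an instillation effect of both gels on the right eye, in SD units; its size is assumed.

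| Subject answers for | rho 0 | 0.5 | 0.8 | 0.95 |
|---|---|---|---|---|
| Treated eye | 0.75 | 0.75 | 0.75 | 0.75 |
| Average of both eyes | 0.46 | 0.33 | 0.28 | 0.26 |
| Worse eye, no shared shift | 0.50 | 0.48 | 0.53 | 0.63 |
| Worse eye, shared shift 0.5 | 0.62 | 0.64 | 0.70 | 0.74 |
| Worse eye, shared shift 1.0 | 0.69 | 0.71 | 0.74 | 0.75 |

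At rho = 1 with no shared shift, averaging gives about 0.26 and worse-eye answers lose nothing (0.75). Repeat runs agree within simulation error, with minima of about 0.25 for averaging and 0.47 for worse-eye answers.

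Healthy subjects may often score zero. With half of comparator eyes at zero and no shared shift, power is about 0.72 (treated eye), 0.47-0.62 (worse eye) and 0.40-0.51 (average).

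**Reading the table.** If both gels are felt on instillation, the right eye tends to be the worse eye in both arms, and worse-eye answers recover almost all the power. Averaging loses power whatever the shared shift, because a shift common to both arms cancels in the comparison.

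**The case against.** - **The ICO is a published, Rasch-scaled 0-100 questionnaire, used here as written in an exploratory phase I study.** Nothing in the documents supports the scaling for one-eye wording. This stands, and makes keeping the published wording defensible. A change made equally in both arms does not bias the comparison between them, however.
- **Subjects with one irritated eye will answer for that eye.** Many may, and then the loss is small or nil. The plan neither secures this nor records it, so it could not be checked afterwards. No document supports averaging as the typical behaviour either.
- **Baseline could remove the left eye.** The ICO is taken at baseline and at the final visit. In change scores under averaging, power is about 74% if the left eye does not change, 66% if its change has half the SD of the right eye's, and 46% if the SDs are equal. This stands only conditionally, since the SAP does not specify a between-arm analysis of ICO change.
- **Other measures cover the treated eye.** Adverse events are co-primary and logged by eye, and the diary review at Visit 1 looks at post-instillation symptoms. An adverse-event difference would block the conclusion; the diary review is not the primary score and does not repair it.
- **The annexed form bears another study's code (SOPH172-0919-I).** The form used may therefore differ. If it already names the eye, the point falls away, but both documents annex this one.

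**Conclusion.** The omission is certain: the sole primary tolerability score is not tied to the treated eye. Its direction under the decision rule is also clear: dilution favours a tolerable conclusion. Its size is unknown. Under the assumed 1.0 SD difference, power falls from about 75% to about 25-46% if subjects average both eyes. For worse-eye answers it lies between about 47% and almost no loss, depending on the between-eye correlation and on any instillation effect shared by the gels.

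Stronger readings do not hold. A reader might infer that the score is biased between arms; it is not when the products are equal. A reader might infer that a stated power is missed; none is stated for the ICO. A reader might take a large worse-eye loss as established; that requires the comparator gel to have no effect of its own on the eye, which the documents do not say. A reader might add that the objective on burning, foreign body sensation and itching has no measure; the signs-and-symptoms heading in Protocol Table 5 may have lost its rows in conversion, so that cannot be concluded.

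This is a cheap improvement worth making, not a defect that invalidates the trial.

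**What to change.** Before the first baseline ICO, add one line to the form's directions, used at baseline and at the final visit: *Answer for your right eye only.* State in SAP Table 2 that the score serves between-arm and within-subject comparison only. The price is a departure from the published scaled wording, equal in both arms.

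If the published wording is kept, add a closing line instead: *My answers refer to: right eye / left eye / both.* Tabulate it by arm. This leaves the scaled items untouched, but only shows how far the problem occurred.

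Either change goes through the amendment route in Protocol 10.2, which covers patient documents and measurement scales. The form has to be reissued under this trial's code anyway, so the added cost is one line.
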